8.4 Exacerbation/Relapse Determination

8.4.1 Criteria to determine recurrences of disease and the need for re-initiation of therapy with plasma exchange will be the same as those to diagnose TTP (section 5.2.1). Patients requiring the reinstitution of plasma-based therapy (plasma exchange or infusion) within the first 30 days after discontinuing PE will be considered to have an “exacerbation” of their TTP.

8.4.2 Patients with a recurrence of TTP at a time point greater than 30 days from the end of plasma exchange therapy will be considered to have a "relapse" for the purposes of this study.

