8.5 Treatment after Recurrences of TTP

8.5.1 Patients suffering exacerbations of TTP as described in the protocol (Section 6.4) after treatment on the corticosteroid arm of this study may then be treated with CSA concurrent with the resumption of plasma exchange at the same dose and schedule as described in the CSA arm of this randomized trial, assuming that they still meet enrollment criteria (including the serum creatinine). Patients will also discontinue the corticosteroids on the same day that CSA is initiated. Patients treated with CSA and PE for exacerbations of TTP will then be prospectively followed as described below (Section 9.3 – 9.5), but will be analyzed independently from the patients treated with CSA and PE as the upfront therapy.

8.5.2 Patients suffering a relapse (recurrence greater than 30 days after the last exchange procedure) whether during CSA or after completing 6 months of CSA will continue to be followed on this study for the purposes of gathering follow-up data, but may be treated at the discretion of the treating physician.

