9.5 Outpatient Visits

9.5.1 After discharge from the hospital, patients will be seen weekly in the outpatient clinic for the first month. Patients will then be seen monthly for the next 6 months, regardless of which arm of the study they were randomized to. After six months of continuous follow-up patients will then be seen every 3 months for the next 3 years to monitor the course of their disease and obtain laboratory follow-up studies (see Appendix 1)

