Additionally, we will evaluate several secondary clinical endpoints through this trial, including: 1) exacerbation rate within 30 days post-PE; 2) clinical response rate; 3) the number of PE procedures required to achieve a clinical response; 4) relapse rate; and 5) safety and tolerability of each of the adjuvant treatments to PE. Each of the rates will be calculated assuming that these endpoints are binomially distributed, and 95% confidence intervals generated. For the exacerbation rate endpoint, we will only include those patients who have achieved clinical response (i.e. excluding refractory patients) and compare these rates between the two arms. We will have at least 80% power to detect a difference if the true exacerbation rates are 55% vs. 90% for this subset analysis (not adjusting for multiple comparisons); however, this comparison is distinctly ancillary to our primary clinical interest of achieving treatment success in all patients treated versus only keeping responding patients from experiencing TTP exacerbation. We will also evaluate relapse as a time-to-event variable, where Kaplan-Meier methods will be used to assess time to relapse from last plasma exchange in responding patients. The number of exchange procedures required to achieve clinical response will be assessed between arms using Poisson regression. Safety and tolerability data will be summarized by type of adverse event with frequencies calculated and compared between arms. In addition to these planned quantitative analyses, we will also use graphical

analyses to assess patterns and differences in these factors between the treatment arms.

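### The relapse rate is planned as a simple binomial proportion with no time window, which is too low if follow-up is incomplete; the planned time-to-event analysis should lead and be fully specified

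*Combined protocol and SAP*

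**What the plan says.** Section 14.2 (Analysis Plan) lists five secondary clinical endpoints, the fourth being the relapse rate, and continues: "Each of the rates will be calculated assuming that these endpoints are binomially distributed, and 95% confidence intervals generated". It gives the relapse proportion no time window and no denominator. Later in the same paragraph it adds: "We will also evaluate relapse as a time-to-event variable, where Kaplan-Meier methods will be used to assess time to relapse from last plasma exchange", restricted to responding patients. It names no time point, confidence interval or between-arm test for that curve. Section 1.2 nevertheless lists relapse rate among the outcomes on which the arms are to be compared.

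Section 8.4 defines relapse by a lower limit only: "Patients with a recurrence of TTP at a time point greater than 30 days from the end of plasma exchange therapy will be considered" as relapsed.

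On follow-up, Section 9.5 gives weekly and then monthly visits "regardless of which arm of the study they were randomized to", and then: "After six months of continuous follow-up patients will then be seen every 3 months for the next 3 years to monitor the course". Appendix 1 runs to week 160. Under Section 8.5, patients who relapse "will continue to be followed on this study for the purposes of gathering follow-up data". The documents give no expected loss rate, no cut-off date for the relapse analysis and no censoring rule.

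**The concern.** A binomial rate suits an endpoint with a fixed window, such as exacerbation within 30 days. Relapse is open-ended. Events divided by patients then depends on how long patients were watched as well as on how often they relapse. A patient lost at one year without relapse counts the same as one followed relapse-free to the end.

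Two consequences follow if follow-up is incomplete. The crude rate falls below the risk over the planned period, and a difference in retention between arms appears as a difference in relapse. The plan would also yield two relapse results, one crude and one from the Kaplan-Meier curve, that can disagree, and it does not say which one counts.

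**Working it through.** **Figure to reproduce.** The documents state no relapse rate, power or sample size. The nearest figure is in Section 14.3: somewhat more than 16 relapses in a little over 400 quarterly observations.

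**Inputs**
- Relapse risk per quarter, from Section 14.3: q = 16/400 = 0.04. With 416 as denominator it is 0.038.
- Horizon, from Section 9.5: 3 years of quarterly visits, 12 quarters. Appendix 1 shows 11 quarterly columns, weeks 40 to 160.
- Loss per quarter, l: **assumed**, 0% to 10%, unrelated to relapse risk. The documents give no value.

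**Step 1: risk over the planned horizon.** This is what a Kaplan-Meier curve estimates when loss is unrelated to relapse.

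1 − (1 − q)^12 = 1 − 0.96^12 = 38.7%

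With q = 0.038 it is 37.5%; over 11 quarters at 4% it is 36.2%. The corresponding 1- and 2-year risks are 1 − 0.96^4 = 15.1% and 1 − 0.96^8 = 27.9%.

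**Step 2: crude proportion under loss.** Let r = (1 − q)(1 − l), the chance of remaining relapse-free and in follow-up through one quarter. The expected crude proportion is q(1 − r^12)/(1 − r).

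- For l = 0.02: r = 0.96 × 0.98 = 0.9408, r^12 = 0.481, so 0.04 × 0.519/0.0592 = 35.1%.
- For l = 0.06: r = 0.96 × 0.94 = 0.9024, r^12 = 0.292, so 0.04 × 0.708/0.0976 = 29.0%.

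| Assumed loss per quarter | Crude proportion | Shortfall from 38.7% (points) |
|---|---|---|
| 0% | 38.7% | 0 |
| 1% | 36.8% | 1.9 |
| 2% | 35.1% | 3.6 |
| 4% | 31.9% | 6.8 |
| 6% | 29.0% | 9.7 |
| 10% | 24.3% | 14.4 |

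**Step 3: difference between arms.** With the same 4% per quarter in both arms, but 2% loss per quarter in one and 6% in the other, the crude rates are 35.1% and 29.0%. The gap of about 6 points comes from follow-up alone.

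**Step 4: do the plan's figures reveal incomplete follow-up?** They do not. Over 11 quarterly visits at 4%, a fully followed patient contributes (1 − 0.96^11)/0.04 = 0.362/0.04, about 9.0 observations before relapse. Four hundred observations therefore fit about 44 fully followed patients (61% of 72), with 44 × 0.362, about 16 relapses. They fit equally well with all 72 patients contributing 400/72 = 5.6 quarters each. The figures cannot separate the two cases.

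**The case against.** The strongest reply is that the plan already contains the remedy. Kaplan-Meier is named in the same paragraph, and neither relapse analysis is ranked above the other. A reader might infer that the binomial figure is the headline result; the documents do not say so, and they attach no between-arm test to either relapse analysis. That part of the reply stands. It leaves the binomial interval as the only relapse interval promised.

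A reader might also infer that patients will certainly have unequal follow-up and that the rate will therefore be understated. The documents do not support this. All patients share one visit schedule, follow-up continues after relapse, and no early data cut is stated. Staggered entry matters only if relapse is analysed before the last patients complete their visits. Incomplete follow-up is nonetheless plausible: the group's earlier cohorts had follow-up of 1 to 25 months (Section 3.2) and 12 to 41 months (Section 3.1), and Section 14.3 allows for samples missing at some time points.

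The effect can also be overstated by mixing horizons. With an assumed hazard of 0.15 per year and follow-up spread evenly over 0.5 to 3.5 years, the crude proportion is 25.3%, and the 3-year risk is 1 − exp(−0.45) = 36.2%. But mean follow-up there is 2 years, and the 2-year risk is 1 − exp(−0.30) = 25.9%. Most of that contrast is the choice of horizon. The table above uses the scheduled 3 years of quarterly visits as its target.

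Nor is the binomial interval invalid in a strict sense: with independent follow-up times it covers the risk averaged over whatever follow-up occurred. That quantity is hard to interpret or to compare across arms. Precision is also limited. With 29 responders in an arm (80% of 36, an assumption), a rate of 38.7% has an approximate 95% interval of 21% to 56%, so a 6-point artefact is small beside sampling error.

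**Conclusion.** The point holds as a conditional one. The plan calculates an open-ended endpoint as a binomial proportion without a window, cut-off or loss rule. With complete follow-up the bias is zero. At the plan's own 4% per quarter, the 3-year proportion is too low by about 2 to 14 points for assumed losses of 1% to 10% per quarter. Losses of 2% against 6% by arm create a false gap of about 6 points.

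These sizes rest on a constant risk, on loss unrelated to relapse, and on loss rates that are not in the documents; nothing there indicates that loss will differ by arm. The 4% comes from anticipated quarterly samples in sustained remission and may not describe the first six months. The defect is minor, affects a secondary endpoint, and leaves the primary analysis and sample size untouched.

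**What to change.** In Section 14.2:

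1. Remove relapse from the sentence on binomial rates and name the time-to-event analysis as the main relapse analysis.
2. Report cumulative relapse from last plasma exchange at fixed times, for example 1, 2 and 3 years, with 95% confidence intervals by arm, and compare arms by log-rank test.
3. State the data cut-off and the censoring rules for loss and withdrawal. Say how corticosteroid-arm patients who move to cyclosporine after an exacerbation (Section 8.5) enter the relapse analysis, since that route exists in one arm only.
4. Treat death without relapse as a competing event and estimate cumulative incidence, or report this as a sensitivity analysis. Kaplan-Meier with deaths censored would overstate the proportion who actually relapse.

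The cost is a few sentences. The visits and the Kaplan-Meier method are already planned, and no extra patients or data are required beyond recording dates of last contact and death.

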14.0 Statistical Analysis

14.1 Statistical Considerations-Sample Size Determination

For the study of the primary endpoint (treatment success rate), the sample size required is calculated based on the data from our previous publications. In these previous studies that looked separately at CSA/PE in 10 patients and at corticosteroids/PE in another 10 patients, we saw promising results that led to our hypothesis that CSA/PE treatment for TTP patients results in greater treatment response. In those studies, the primary endpoint was the proportion of patients who had TTP exacerbation, which is a more stringent endpoint that does not include other types of treatment failures such as refractory patients and/or death within 30 days post-PE. In the previous published pilot studies, we showed that 6/10 corticosteroid-treated patients exacerbated versus 0/10 CSA-treated patients. Combined with experience with subsequently treated patients, we observed an overall treatment success rate of 80% and 83% in refractory vs. de novo TTP patients, respectively, treated with CSA+PE versus 33% in those treated with corticosteroids+PE.

In terms of our primary endpoint of treatment success rate, we have designed a phase III trial that compares the proportion of treatment successes in each arm. Specifically, this study design will have at least 80% power to determine a significant difference in the treatment success rates between the arms if the true rates are 50% vs. 80%, assuming a significance level of 0.05 and a two-sided test. This reflects a clinically meaningful difference, and the data from our previous studies and experience support it as a feasible difference to detect. We plan to enroll a total of 72 patients to this trial (36 to each arm) to test the null hypothesis that there is no difference in treatment success rate between these treatments.

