To examine the potential of the 4 indices (ADAMTS13 activities, ADAMTS13 antigen levels, ADAMTS13 (IgG) autoantibody levels, and antibody inhibitor titers) to predict the recurrences of TTP, we will use the longitudinal data in two ways by separating indices obtained during the sustained clinical remission when they are measured every three months (quarterly) from those indices measured during the initial clinical response when patients are monitored weekly. The data for the relapse analysis will come from all quarterly samples collected from qualified study subjects during sustained remission. The outcome of interest will be whether or not the

individual experiences a relapse of TTP during the three months following the date the measurements are taken. We anticipate obtaining a total of >400 observations that will correspond to approximately >16 events of relapse and other quarterly measurements ($n \sim 400$) without relapses. For analysis of exacerbation in initial clinical remission, the outcome of interest will be whether or not the individual experiences an event of exacerbation in the week following the measurement. The weekly samples in initial clinical remission from the same group of study subjects will be analyzed. We anticipate a total of about 200 weekly data points, corresponding to about >16 measurements with events of exacerbation and 200 measurements without events in the week following measurement. We will use the logistic regression model to analyze all 4 indices independently as well as to evaluate their interacting effects.

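### Responders who die without a TTP recurrence count as non-events in the binomial exacerbation and relapse rates, and the Kaplan-Meier analysis of relapse has no rule for death

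*Combined protocol and SAP*

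**What the plan says.** Both events are defined in section 8.4. For exacerbation: "Patients requiring the reinstitution of plasma-based therapy (plasma exchange or infusion) within the first 30 days after discontinuing PE will be considered" to have one. For relapse the subject is "Patients with a recurrence of TTP at a time point greater than 30 days from the end of plasma exchange therapy". Death is part of neither definition.

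Section 14.2 lists the exacerbation rate and the relapse rate as secondary endpoints and gives one method for all the rates: "Each of the rates will be calculated assuming that these endpoints are binomially distributed, and 95% confidence intervals generated". For exacerbation it sets the population: "For the exacerbation rate endpoint, we will only include those patients who have achieved clinical response (i.e. excluding refractory patients". Refractory patients leave the denominator; responders who die are not mentioned. Relapse gets a second analysis: "Kaplan-Meier methods will be used to assess time to relapse from last plasma exchange in responding patients". No censoring rule or competing event is named.

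In the marker models of section 14.3, for exacerbation, "the outcome of interest will be whether or not the individual experiences an event of exacerbation in the week following the measurement"; the relapse models do the same for the next quarter. An interval that ends in death is not addressed.

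Death does appear elsewhere. Section 14.1 says of the pilot studies' exacerbation endpoint that it "does not include other types of treatment failures such as refractory patients and/or death within 30 days post-PE", which implies that such deaths are failures under treatment success. Section 10.1.2 makes a fatal event a serious adverse event, and 14.2 compares adverse event frequencies between arms.

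**The concern.** A death without recurrence ends the chance of an exacerbation or relapse, but in a binomial rate it is counted in the same way as a patient who stays well. If one arm loses more responders, its two secondary rates fall for that reason alone. Equal mortality cannot be taken for granted, because exposure differs by arm: roughly eight weeks of corticosteroid (7.2.2) against six months of cyclosporine (7.3.2).

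For relapse the time span adds to this. Follow-up runs every three months for three years (9.5.1; calendar to week 160 in Appendix 1), while the deaths that 14.1 mentions are those within 30 days of the last exchange. No efficacy endpoint in the plan counts a later death without recurrence.

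Also at stake is consistency. The binomial relapse rate keeps a dead patient as a non-relapser, while a standard Kaplan-Meier analysis would remove that patient from the risk set at death. The same death would then push the two relapse estimates in opposite directions.

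**Working it through.** **The plan's own figure.** Section 14.2 claims at least 80% power for 55% vs 90% in responders. With the pooled-variance formula, power = Φ[(d√n − 1.96√(2p̄q̄)) / √(p₁q₁ + p₂q₂)], where d = 0.35 and p̄ = 0.725:
- n = 25 per arm: 81.1%
- n = 30 per arm: (0.35 × 5.477 − 1.96 × 0.6315) / 0.5809 = 1.169, so 87.9%

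The claim is reproduced, and it does not depend on how death is handled. I read 55% and 90% as exacerbation-free rates (45% vs 10% with the event), which fits the pilot results of 60% vs 0%; the power is the same either way.

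**Responders per arm.** Section 2.6 reports remission in 10/12 on corticosteroids, and section 3.2 in 11/12 on cyclosporine. With 36 per arm: 36 × 10/12 = 30 and 36 × 11/12 = 33.

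**Size of one death.** 1/30 = 3.3 points; 1/33 = 3.0 points.

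**Range.** The documents give no death rate in responders. The one mortality figure, 2.4% (section 2.1), comes from a series on complications of plasma exchange. Carried over in full it gives 0.024 × 30 = 0.7 and 0.024 × 33 = 0.8 deaths. I assume 0 to 3 in one arm: 3/33 = 9.1 points and 3/30 = 10 points at the top, which is about four times that figure.

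**Effect on the exacerbation comparison (illustrative counts, Fisher's exact test).** Start from 13/30 (43.3%) vs 3/33 (9.1%) and count deaths without recurrence as events.

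| Deaths, steroid / CSA | Exacerbation or death | p |
|---|---|---|
| 0 / 0 | 13/30 vs 3/33 | 0.003 |
| 0 / 1 | 13/30 vs 4/33 | 0.009 |
| 0 / 2 | 13/30 vs 5/33 | 0.024 |
| 0 / 3 | 13/30 vs 6/33 | 0.053 |
| 2 / 2 | 15/30 vs 5/33 | 0.006 |

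Only the lopsided case at the top of the range crosses 0.05. Equal deaths in both arms change little.

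**Effect on relapse at 3 years.** Assume constant hazards: relapse 0.10 per year, death without relapse 0.05 per year.
- 1 − Kaplan-Meier, deaths censored: 1 − exp(−0.30) = 25.9%
- Cumulative incidence: (0.10/0.15) × [1 − exp(−0.45)] = 24.2%
- Relapse or death: 1 − exp(−0.45) = 36.2%

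With complete follow-up the binomial rate estimates the 24.2%. Hold the relapse hazard at 0.10 and vary the death hazard over 0.02, 0.05 and 0.10: cumulative incidence is 25.2%, 24.2% and 22.6%, while the censored Kaplan-Meier figure stays at 25.9%. So more deaths lower the binomial rate, and censoring overstates the incidence that patients actually experience.

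**The case against.** The best reply is that the important deaths are already handled. Section 14.1 implies that death within 30 days is a failure in the primary endpoint, which covers all treated patients, and 14.2 calls the exacerbation comparison ancillary to it. Exacerbation-or-death in responders partly repeats that endpoint in a subset. This stands, and it keeps the point modest. It does not help with deaths after 30 days.

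Several stronger readings are tempting, and the documents do not support them:
- A reader might infer that death counts nowhere outside the primary endpoint. Fatal events are serious adverse events, the reporting form in Appendix 3 records death, adverse events are compared between arms, and the DSMB sees safety data at the interim analysis.
- A reader might infer that every death escapes the two rates. A diagnosed TTP recurrence after day 30 is a relapse under 8.4.2 even if fatal, and 8.4.1 turns on a need for plasma therapy. Also, 8.1 asks that remission be maintained after the taper, so some early deaths may not be responders. The clear non-events are deaths without a recognised recurrence.
- A reader might take the remark in 14.1 as this trial's rule for exacerbation. It describes the pilot endpoint.
- A reader might infer that Kaplan-Meier counts deaths as relapse-free, or that 14.3 codes them as zero. The plan states neither. Censoring, if used, works in the opposite direction to the binomial rate.

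It is also fair to say that exacerbation alone and exacerbation-or-death are different quantities, so the gap between them is not an error in either. The trouble lies in reporting the first without the second.

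**Conclusion.** The concern holds for the two binomial rates: under 8.4 and 14.2, a responder who dies without recurrence stays in the denominator as a non-event. For the Kaplan-Meier analysis of relapse and the 14.3 models the finding is that no rule is given, and that the default for Kaplan-Meier would contradict the binomial analysis.

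The size is about 3 points per death, and 0 to 10 points for 0 to 3 deaths in one arm. This rests on the pilot response rates and on an assumed number of deaths. At the likely end, about one death, a planned difference of 35 points would survive. No stated power or sample size changes. That objective 1.1 names exacerbation while 14.1 makes treatment success primary is a separate matter and is not used here to raise the weight. The change is worth making because it is cheap, and because a rule chosen after the deaths are known could follow the results.

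**What to change.** - **14.2, exacerbation.** In responders, report exacerbation or death within 30 days after the last exchange, with exacerbation alone beside it.
- **14.2, relapse.** Report cumulative incidence of relapse with death as a competing event, plus Kaplan-Meier for relapse-or-death.
- **14.3.** Do not code an interval cut short by death without recurrence as event-free. Exclude it, and add a sensitivity analysis that counts it as an event. The rule should not depend on cause of death, since the protocol describes no adjudication of cause.

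The cost is a few sentences in the analysis plan and some extra output. The composites need only the date of death and the recurrence data that follow-up already provides. The drawback is that the composites include some deaths unrelated to TTP, which is why the components are shown separately.

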7.0 Treatment Plan: Initial Therapy

7.1 Therapeutic Plasma Exchange-Both Study Arms

7.1.1 Plasma exchange will be started as soon as the diagnosis of TTP has been made. (section 5.2.1). As it is important to institute therapy as soon as possible, patients will not have therapy delayed while obtaining informed consent.

7.1.2 Plasma exchange will be performed daily with one plasma volume exchanged using plasma as the replacement fluid until a complete remission is obtained (see response criteria 8.0).

7.1.3 Patients will receive either prednisone or cyclosporine orally as an adjunct to PE depending on the outcome of randomization (see sections 7.2-7.3 below). Therapy with these adjuncts will be initiated concurrent with and continue throughout plasma exchange therapy as described below.

7.1.4 After a complete remission (see response criteria 8.0) has been attained patients will have one exchange performed every other day for a total of 2 more exchanges, with the first day that the platelet count and LDH are normal counting as the first of the two exchanges.

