8.2 Partial Response

8.2.1 Patients showing improvement (increase in platelet count and a decrease in the LDH, but not meeting the full criteria for complete remission) should continue concurrent CSA or prednisone and plasma exchange therapy for up to 4 weeks. If at that time patients still have not met the criteria for remission, patients will be considered to have been unable to achieve remission but will remain on this protocol for the purposes of data and clinical sample collection and for safety monitoring, but may be treated at the discretion of their treating physician.

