8.3 Refractory Disease

8.3.1 Patients not showing signs of improvement (partial or complete response) or benefit with daily plasma exchange and CSA therapy after 1 week of continuous therapy should be considered to have refractory disease. These patients will remain on this protocol for the purposes of data and clinical sample collection and for safety monitoring, but may be treated at the discretion of their treating physician and will be considered to have failed therapy.

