14.3 Statistical Considerations-Correlative Laboratory Studies

The correlative biomarker outcomes described above will be descriptively summarized across and within treatment arms, and patterns in these changes in biomarkers and how they relate to treatment success, relapse, and TTP exacerbation will be explored graphically. For the study to determine the effects of corticosteroids and cyclosporine given individually on serial measurements of ADAMTS13 biomarker profiles and VWF multimeric patterns after their initial therapy and throughout longitudinal follow-up, we will evaluate these biomarkers in relation to the clinical outcomes of interest. For treatment success rates, we will evaluate baseline levels of these biomarkers to identify if there are any associations between these biomarkers and how these patients respond to treatment. These will first be explored graphically, also denoting those patients in the two different treatment arms. Logistic regression for whether or not the patient had a treatment success will be modeled with these baseline biomarkers as well as treatment arm.

In addition, we will compare the changes for each biomarker between the two groups. TTP exacerbations and relapses will be modeled separately. Both of these events are preceded by a period of clinical response where patients exhibit resolution of clinical signs and normal laboratory values. However, as stated above, there are important differences that warrant modeling TTP exacerbation and TTP relapses independently. First, the frequencies of specimen collection are different between the observation periods that lead to the exacerbation and relapses. The patients in the period of initial clinical response are monitored weekly, while the patients in the sustained clinical remission are followed quarterly. Secondly, the underlying pathophysiology for exacerbation and relapse are likely to be different. The disease exacerbation probably represents a continuation of an incompletely resolved disease while relapses of TTP most likely represent a de novo episode of TTP. As a result, the biomarkers that predict TTP exacerbation and relapse are likely to be different.

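### The section 14.2 gloss on clinical response keeps partial responders who never remit in the exacerbation denominator, and their primary-endpoint status is not stated

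*Combined protocol and SAP*

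**What the plan says.** Section 8 of the combined protocol and SAP defines complete remission (8.1), partial response (8.2) and refractory disease (8.3). It has no entry for clinical response, the term used for the secondary endpoints in 14.2.

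- **Section 14.2**, on the exacerbation rate: "we will only include those patients who have achieved clinical response (i.e. excluding refractory patients". The same section also lists the clinical response rate and the number of exchanges to clinical response, and runs the Kaplan-Meier relapse analysis in responding patients.
- **Section 8.3.1**, on who is refractory: "Patients not showing signs of improvement (partial or complete response) or benefit" after 1 week. These patients "will be considered to have failed therapy".
- **Section 8.2.1**, on partial response: "increase in platelet count and a decrease in the LDH, but not meeting the full criteria for complete remission". If this is still so at 4 weeks, "patients will be considered to have been unable to achieve remission but will remain on this protocol".
- **Section 14.3**, on exacerbation and relapse: "Both of these events are preceded by a period of clinical response where patients exhibit resolution of clinical signs and normal laboratory values".
- **Section 7.1.2**: daily PE continues "until a complete remission is obtained (see response criteria 8.0").
- **Section 14.1** mentions, as outcomes the earlier exacerbation endpoint left out, "other types of treatment failures such as refractory patients and/or death within 30 days post-PE". Treatment success itself is not formally defined.

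**The concern.** The parenthesis in 14.2 equates responder with not refractory. The description in 14.3 is much closer to remission. The two part company for one kind of patient: improved enough not to be refractory, but not in remission at 4 weeks. No minimum improvement is set, so any platelet rise with any LDH fall qualifies.

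Under 14.2 this patient is a responder and enters the exacerbation denominator, normally without having had a PE-free period in which an exacerbation could be seen. The rate is then diluted. The response rate, the exchanges to response and the relapse set depend on the same term.

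On the primary endpoint the patient's status is unwritten. Section 8.2.1 lacks the failure label that 8.3.1 carries, and 14.1 does not name the category. The trial is open-label (section 1.0), so a rule left open could be settled with the arm known.

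**Working it through.** **1. The plan's own sample size.** Section 14.1: 50% vs. 80%, two-sided 0.05, 36 per arm, at least 80% power. With unpooled variance:

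z = 0.30 / √[(0.5×0.5 + 0.8×0.2)/36] − 1.96 = 0.30/0.1067 − 1.96 = 0.85, so power is 80.3%.

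The figure reproduces with this formula and is the baseline for step 5. (The pooled formula gives 77.2% at 36 per arm; that is a separate matter.)

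**2. Classification of a patient with partial response only at 4 weeks.**

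| Source | Status |
|---|---|
| 14.2 parenthesis with 8.3.1 | not refractory, so a responder |
| 14.3 | laboratory values not all normal, so normally not a responder |
| Pilot, section 2.6 | not in the denominator: 6/10 remitters, not 6/12 treated |
| 8.2.1 | did not achieve remission; no failure label |
| 14.1 | not named in an open list |

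**3. Historical success rates in 14.1.** Counting as success a remission without exacerbation, over all treated:

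- corticosteroids (section 2.6): (10 − 6)/12 = 4/12 = 33%
- CSA for exacerbation or refractory disease (section 3.1): (9 − 1)/10 = 8/10 = 80%
- upfront CSA (section 3.2): 10 evaluable remitters, 0 exacerbations, 10/12 = 83%

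All three agree with the stated 33%, 80% and 83%.

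**4. Size for the secondary endpoints.** The documents give no frequency of partial response. Assume 2 to 5 patients among 36 per arm.

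- Response rate: 2/36 = 5.6 points to 5/36 = 13.9 points higher under the 14.2 wording.
- Exacerbation rate, illustrative arm with 31 remitters and 14 exacerbations: 14/31 = 45.2%. Adding 2 partial responders gives 14/33 = 42.4%; adding 5 gives 14/36 = 38.9%.
- Power of the subset comparison: assume 30 remitters per arm and read the 55% vs. 90% in 14.2 as exacerbation-free, i.e. exacerbation 45% vs. 10%. With k partial responders added as non-exacerbators, each rate is multiplied by 30/(30 + k):

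| Partial responders added | Rates | Pooled power |
|---|---|---|
| none | 45% vs. 10% | 87.9% |
| 3 per arm | 40.9% vs. 9.1% | 86.5% |
| 6 per arm | 37.5% vs. 8.3% | 85.3% |
| 6 in the steroid arm only | 37.5% vs. 10% | 74.8% |

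**5. Size for the primary endpoint.** One patient is 1/36 = 2.8 points. Assume 50% vs. 80% holds when partial responders count as failures, and ask what happens if they were counted as successes (unpooled formula of step 1):

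| Counted as successes | Rates | Power |
|---|---|---|
| none | 50% vs. 80% | 80.3% |
| 3 per arm | 58.3% vs. 88.3% | 86.4% |
| 3, steroid arm only | 58.3% vs. 80% | 53.5% |
| 3, CSA arm only | 50% vs. 88.3% | 97.2% |

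**The case against.** Much of the plan points towards remission as the intended meaning. The pilot sections report exchanges to remission, daily PE is tied to remission, and 14.3 uses initial clinical response and initial clinical remission for the same weekly-sampled period. The 14.2 parenthesis is attached to the exacerbation denominator only, and the plan calls that comparison ancillary. This lowers the stakes, but the only explicit inclusion rule for that comparison still retains partial responders.

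Three stronger readings are tempting and are not supported:

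- **That a partial responder cannot exacerbate.** Section 8.4.1 defines exacerbation as plasma therapy restarted within 30 days of stopping PE and does not require prior remission. After 4 weeks treatment is at the physician's discretion, so PE could be stopped and restarted. Only the usual course leaves no window.
- **That the pilot figures prove the success rule.** Section 14.1 pools later patients and gives no denominators, and section 2.6 does not say whether the two non-remitters were partial responders, refractory or dead. The match in step 3 is consistent with a remission-based rule, no more.
- **That the plan counts partial responders as primary successes.** No text says so. Section 8.2.1 records that they did not achieve remission, and the 14.1 list is introduced as examples.

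A further point stands and shapes the fix. The 14.3 description is not identical to 8.1, which asks only for neurologic improvement and a creatinine that is not higher. Section 8.1 also requires its criteria to persist after the PE taper. Used unaltered as the responder definition, it could remove exacerbators from their own denominator.

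**Conclusion.** The concern holds as a conflict of definitions. The inclusion rule in 14.2 admits partial responders without remission, against the description in 14.3 and the remitter-only denominator of the pilot, and it yields a diluted exacerbation rate. The plan also leaves unsaid whether such patients are failures on the primary endpoint.

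The sizes rest on an assumed 2 to 5 such patients per arm. If they are few and balanced, the effect on the exacerbation comparison is modest: about 1.4 points of power with 3 per arm (87.9% − 86.5%). The primary endpoint is more sensitive, but large changes there need both an imbalance between arms and a decision to count these patients as successes, neither of which the documents state. The point should be settled before analysis; it does not undermine the design.

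**What to change.** These changes concern analysis definitions only; treatment is unaffected.

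1. In 14.2, define clinical response as first meeting the 8.1 platelet, LDH, creatinine and neurologic criteria within 4 weeks of enrollment. Leave out the 8.1 clause on maintenance after the taper, so that patients who later exacerbate stay in the denominator.
2. Extend the 14.2 parenthesis to exclude partial responders not in remission by 4 weeks as well as refractory patients.
3. Use this definition for every response-based secondary endpoint: response rate, exchanges to response, exacerbation rate and the Kaplan-Meier relapse set.
4. State that patients not in remission at 4 weeks under 8.2.1 count as treatment failures for the primary endpoint, as refractory patients do under 8.3.1.
5. Report partial response as a separate descriptive category.

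The cost is a few sentences and no new data. The reported response rate becomes slightly less favourable.
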